6.4.8 Adherence

Comparison Group

Participants agree to oral administration of 600 IU vitamin D once per day. Participants must agree to abstain from ingesting oral vitamin D supplements. Participants must also have blood drawn at baseline, day 70, and at day 100.

Treatment Group

Participants must be exposed once every other week (14 days +/- 24 hours). Participants must agree to abstain from ingesting oral vitamin D supplements. Participants must also have blood drawn at baseline, day 70, and at day 100.

In this pilot feasibility study, one aim is to evaluate acceptability and adherence.

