6.1 Overall Study Design and Plan

This non-inferiority study used a prospective, longitudinal, randomized design with repeated measures to address vitamin D sufficiency in AD, retiree, beneficiary, and DA civilian populations. It is important and necessary to conduct this study with adult humans, military personnel in particular, to determine acceptability and feasibility of this phototherapy kiosk as an addition to existing Warfighter resources to promote health and resilience. Following Madigan Army Medical Center (MAMC) Institutional Review Board Human Subjects and Ethics approval, the SPK will be installed in a location approved by the Radiation Safety Officer, the study team will be hired, and recruitment will begin for an anticipated 12-month project period. Approximately 120 volunteers will be approached from MAMC and Joint Base Lewis-McChord (JBLM), a large joint base in the Pacific Northwest, where over 25,000 Soldiers and Airmen train every day and regional beneficiaries' number ~98,000. Recruiting efforts will attempt to capture a representative sample of the population including both genders, diverse ethnicities, and a range of age (18-70 years) and body mass index (BMI), who have no contraindication for UVB exposure or oral vitamin D supplementation. In addition to walk-in volunteers, the research team will attend the JBLM Newcomer's Orientation. Using a computer-generated block design, volunteers will be randomized to one of two groups by the research pharmacist; 1) oral vitamin D supplementation, or 2) standing phototherapy kiosk with UVB exposure, for a 10-week period.

Comparison Group (CG) – Supplement

A MAMC research pharmacist will dispense a 70-day supply of the vitamin D3 600 IU oral supplement to subjects assigned to this group. The Project Director will work with the pharmacist to coordinate pick-up of supplement bottles for subjects or optimal in-person dispensing times.

Treatment Group (TG) – Phototherapy

The Project Director provides oversight for the phototherapy treatment. The kiosk will deliver the UVB dose under supervised conditions over a 1 – 10 minute interval based on the Fitzpatrick skin type with the subject wearing minimal or no clothing, preferably no more than a bathing suit, and protective eye-wear. The experience in the SPK was designed to be comfortable and user-friendly.

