6.4 Treatments

6.4.1 Treatments Administered

Comparison Group - Supplement

Volunteers assigned to this group are provided with a 10-week supply (70 pills) of a vitamin D3 supplement. Consented participants are instructed to take one 600 IU pill by mouth each day for ten weeks. They are instructed to take this with a meal. This dose is the RDA for adults between 18 and 69 years old according to the Institute of Medicine Committee to Review Dietary Reference Intakes for Vitamin D and Calcium.²⁰

Treatment Group - Phototherapy

Volunteers assigned to this group are administered phototherapy treatments once every other week, for 10 weeks. The treatment usually lasts no more than 10 minutes and is based on the Fitzpatrick skin type classification tool¹⁹ which is self-assessed via the computer touch screen in the kiosk.

Table 1. Study Summary

Phase	Initial (T)	Time 1 (T+1wk)	Time 2 (T+3wk) Time 3 (T+5wk) Time 4 (T+7wk) Time 5 (T+9wk) Time 6 (T+11wk)	Time 7 (T+15wk)
Screening	X			
Informed Consent	X			
Submit Blood Tests	X		X (Time 6)	X
Randomization	X			
Demographics and Surveys		X	X (Time 6)	
Inbody		X		
Treatment -Phototherapy (every other week x6)		X	X (Time 6 = Final Exposure)	
Device Usability Scale - Phototherapy			X (Time 6)	
Treatment -Vit D Supplement (daily for 10 weeks)		X	X	

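### Adherence is named as an aim, but no measure of pill-taking is described for the supplement arm; unrecorded missed pills could bias the comparison toward non-inferiority of the kiosk

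*Combined protocol and SAP*

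**What the plan says.** Section 6.4.8 closes with "In this pilot feasibility study, one aim is to evaluate acceptability and adherence". For the supplement arm the same section gives an undertaking: "Participants agree to oral administration of 600 IU vitamin D once per day". It adds that participants abstain from other vitamin D supplements and attend the blood draws. Section 6.4.1 says "Consented participants are instructed to take one 600 IU pill by mouth each day for ten weeks", and section 6.1 says the research pharmacist "will dispense a 70-day supply of the vitamin D3 600 IU oral supplement". The one mention of bottles, "The Project Director will work with the pharmacist to coordinate pick-up of supplement bottles for subjects", concerns handing them out, not getting them back.

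For the other arm, section 6.1 says "The kiosk will deliver the UVB dose under supervised conditions". Section 6.4.2 describes software that identifies the user and manages exposure time and frequency. Sections 6.4.4 and 6.4.5 fix six sessions at 14-day intervals.

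Section 6.5.1 tracks screening, enrolment, completion of timepoints and dropout by arm. The questionnaire updated at 10 weeks covers current medications, diet and sun exposure, but not study doses taken or missed. Section 6.6.1 analyses everyone with a valid baseline and at least one follow-up draw. It sets no adherence criterion and no per-protocol set.

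**The concern.** The trial is described throughout as non-inferiority, with the supplement as active control (section 6.2) and no untreated arm. In such a trial the control must actually deliver its effect. If pills are missed, the control response falls and the kiosk has a lower bar to meet.

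The plan would observe exposure in one arm only. In Table 1, Times 1 to 6 are the six phototherapy sessions, so a completed timepoint in the kiosk arm is a dose received. In the supplement arm a completed timepoint shows only that the person attended.

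The outcome cannot fill the gap. Serum 25(OH)D is the endpoint itself, and section 6.4.7 leaves sun exposure and dietary vitamin D uncontrolled. A control arm with a small rise could reflect missed pills, little sun, or a weak effect of the supplement. Without dose data, the report could neither describe adherence to the comparator nor build a per-protocol comparison.

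**Working it through.** The plan gives no figure for adherence, so there is none to reproduce. Its only sample-size arithmetic, 60 × 1.30 = 78, does not bear on this point; the required 60 is used below only to set an arm size.

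**Step 1. Shift in the comparison.** Assumptions, none given in the documents: full adherence raises 25(OH)D by E = 4 to 8 ng/mL, and the rise is proportional to the share a of pills taken.

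Loss of control effect = (1 − a) × E

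| Share of pills taken | E = 4 | E = 8 |
|---|---|---|
| 80% | 0.20 × 4 = 0.8 ng/mL | 0.20 × 8 = 1.6 ng/mL |
| 70% | 0.30 × 4 = 1.2 ng/mL | 0.30 × 8 = 2.4 ng/mL |
| 50% | 0.50 × 4 = 2.0 ng/mL | 0.50 × 8 = 4.0 ng/mL |

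The kiosk-minus-supplement difference rises by these amounts. The direction is the same whether the kiosk is truly worse, equal or better.

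**Step 2. What such a shift could do to a test.** The plan states no margin, alpha or SD. Further assumptions: one-sided 0.025, SD 6 to 10 ng/mL, 30 per arm (the required 60 split equally; the ratio is not stated), and a normal approximation. Set the kiosk truly worse than fully taken pills by exactly the margin M, the boundary case.

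- Expected difference at adherence a: (E − M) − aE = (1 − a)E − M.
- Non-inferiority is declared when the estimate exceeds −M by 1.96 standard errors, so M cancels.
- Chance of declaring it = Φ((1 − a)E / SE − 1.96), with SE = SD × √(2/30).

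Worked ends of the range at 80% adherence:

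- E = 4, SD = 10: SE = 2.58; 0.8/2.58 − 1.96 = −1.65; chance 4.9%.
- E = 8, SD = 6: SE = 1.55; 1.6/1.55 − 1.96 = −0.93; chance 17.7%.

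| Share of pills taken | Chance of declaring non-inferiority, over E = 4–8 and SD = 6–10 |
|---|---|
| 100% | 2.5% |
| 80% | about 5% to 18% |
| 60% | about 9% to 54% |
| 50% | about 12% to 73% |

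These results do not depend on the missing margin, but they do depend on E, SD, arm size and the boundary assumption.

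**Step 3. Can the fix use existing visits?** Table 1 places Time 1 at week 1 and Time 6 at week 11. That is 10 weeks, or 70 days, which matches the 70 pills. Bloods and surveys are already scheduled at Time 6 for both arms.

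**The case against.** Several objections have force.

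- *The aim may concern the kiosk only.* Adherence is not among the three numbered aims in section 5. The sentence in 6.4.8 follows the treatment-group paragraph and pairs adherence with acceptability, which is assessed only in the kiosk group. This is a fair reading. But 6.4.8 covers both arms under one heading, and the active control's exposure matters to the comparison however the aim is read.
- *Failure would not be wholly invisible.* Blood is drawn in both arms at baseline, 10 and 14 weeks, section 6.5.3 expects both to rise, and sun and diet are surveyed. A flat control arm would be a warning. It would be indirect and confounded, and no substitute for a count.
- *Missed pills may be part of the question.* For a self-care device, comparing assigned regimens whatever the adherence is legitimate. The plan does not say this is its target, and adherence would still need reporting to interpret the result.
- *Missed kiosk sessions bias the other way.* True, but timepoint tracking would show them.

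A reader might go further and infer that poor pill-taking would produce a false non-inferiority result. The documents do not support that. It needs material non-adherence, a kiosk truly worse than fully taken pills by at least the margin, and a defined test. Actual adherence is unknown and no margin or alpha is stated. Nor do missed pills always draw the arms together: they do so only if the kiosk is worse, and otherwise the gap in its favour widens. That kiosk sessions are logged is also an inference from supervision, the software description and timepoint tracking; the text does not say so.

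**Conclusion.** The omission stands. Followed as written, the plan yields no data on pill-taking in the active control, while exposure in the kiosk arm is supervised and can be recovered from attendance. Missed pills could bias the comparison toward non-inferiority, and serum 25(OH)D cannot reveal the cause.

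The direction follows from the design, provided the pills raise 25(OH)D at all. The size does not: the ng/mL shifts rest on an assumed 4 to 8 ng/mL effect with proportional response, and the error rates also on an assumed SD, arm size, alpha and boundary case. They show that the gap could matter, not that it did. For a pilot without a stated margin, this is a change that should be made, not evidence that the conclusion would be wrong.

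**What to change.** 1. In Table 1 and section 6.4.8, ask supplement participants to bring their bottle to Time 6 and record the pills left out of 70. Interpret the count with the dispensing and visit dates, because the supply matches the planned period exactly and an early or late visit changes the expected remainder.
2. Record kiosk sessions received out of 6 as a data item.
3. Report adherence by arm.
4. In section 6.6.1, add a supportive per-protocol comparison beside the all-available-data analysis, with an adherence definition stated in advance for each arm. At least 80% of pills (56 of 70) and at least 5 of 6 sessions (83%) would be one example; these are similar cuts, not identical ones. Agreement should not be a condition for the claim, but any disagreement should be discussed before non-inferiority is claimed.

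The cost is one table row and a count at a visit already scheduled. Pill counts can be gamed, and the per-protocol set is smaller and not protected by randomisation, which is why it should stay supportive. The title page gives a completion date of 11 March 2019. If no counts were kept, the report should state this as a limitation on any non-inferiority claim.

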6.5 Efficacy and Safety Variables

6.5.1 Efficacy and Safety Measurements Assessed

To determine that phototherapy is at least equivalent to D3 oral intake to raise or maintain serum 25(OH)D levels over a 10-week intervention period baseline 25(OH)D levels are obtained.

Blood draws will occur upon enrollment with two follow-up measurements, one at 10 weeks and a final level 4 weeks after completing the protocol to evaluate sustainment of the post-treatment level. Serum concentration of 25(OH)D is the best indicator of vitamin D status as it represents cutaneous production and consumption of food and supplements. Serum 25(OH)D has a circulating half-life of 15 days.²⁸ Serum 25(OH)D levels do not indicate the amount of vitamin D stored in body tissues.¹⁰ All blood levels will be obtained by experienced phlebotomists in the hospital central laboratory. There will be no standardization of time of day for the blood draw. An Endocrine consultant will review all abnormal lab values [(25OH)D, PTH, Calcium] and recommended follow-up with the Primary Care Manager, if necessary.

To determine acceptability and feasibility of the standing phototherapy kiosk, a Device Usability Scale will be administered to the Kiosk Group upon completion of the study. This 12-item Likert-type scale was adapted from the Digital Equipment Corporation "System Usability Scale" (1986). Questions assessed cleanliness, ease of use, and comfort of the kiosk with a Likert-type scale where 1= Strongly disagree to 5 = Strongly agree.

The research team will meticulously track the number of potential participants screened, the number of enrolled subjects, completion of all study timepoints, and attrition from each arm.

To examine the relationship of demographic variables, including gender, age, body mass index, body fat, ethnicity, and sun exposure to serum 25(OH)D levels in both groups, several other measurements will be obtained including the following:

1. Body height (Ht) – Vertical height is measured at baseline using a Harpenden Stadiometer and recorded to the nearest 0.1 cm. The stadiometer is composed of a rigid vertical backboard with an attached rigid horizontal headboard which moves up and down the backboard. Final height was the average of two measurements taken by trained study staff.

2. Body weight (Wt), Body fat (BF)/lean mass (Fat free mass), Basal metabolic rate – weight in pounds, percent fat mass and % lean mass, and metabolic rate at rest. The study team will utilize bioelectrical impedance analysis (BIA) to obtain body composition measures. The InBody 230 lean and fat mass assessment device has been shown to be comparable to the gold standard, Dual-energy X-ray Absorptiometry (DXA). It is maintained in the office suite where the project team is located; all team members are trained in its use.
3. Demographic Questionnaire – Is administered at baseline and will be updated at 10 weeks. This tool was created specifically for the study to document relevant personal and family history related to diet, medical conditions, stress fracture history, alcohol and tobacco use, and exposure to sunlight. It is critical to know the presence of any of the following habits or conditions: current medications, age, gender, ethnicity, and race. The tool also covered physical activity and environmental exposures.
4. Vitamin D and Calcium Intake and Frequency Questionnaire²² – This questionnaire is administered in-person by study team at baseline. It is used to record average daily and weekly servings of foods high in vitamin D and/or calcium. The tool has been validated for use in young adults. Permission was obtained from the author for its use. The tool is designed as an Excel worksheet with built-in calculations that total the amounts of vitamin D and calcium in foods that are consumed on a daily or weekly basis. The reference for the nutrient values is the Academy of Medicine. The tool was modified slightly to capture vitamin D and calcium-containing foods and quantities consumed from Northwest sources, such as salmon and ultraviolet irradiated mushrooms.
5. Serum biomarkers - Calcium and Parathyroid Hormone – standard blood tests performed at the same time as the 25(OH)D in order to provide a clinical interpretation in the setting of abnormal levels.

6.5.2 Appropriateness of Measurements

The Elecsys Vitamin D Total II assay is intended for the quantitative determination of total 25-hydroxyvitamin D in human serum and plasma. The electrochemiluminescence binding assay is intended for use on Elecsys and cobas e immunoassay analyzers.

Body composition measurements, biomarkers, and demographic questionnaires all represent valid and reliable methods to capture data relevant to a vitamin D investigation. All measures have been previously tested and used by this research team.

6.5.3 Primary Efficacy Variable(s)

Serum 25(OH)D level is the primary endpoint used to establish whether the treatment in the phototherapy kiosk group is equivalent to the oral vitamin D3 supplementation currently prescribed as the standard of care. It is expected that the serum 25(OH)D levels in both groups will rise over time and that the serum 25(OH)D levels will be equal to, or not less than, that of the oral supplementation group.

A Device Usability Scale will be administered to the Kiosk Group to assess acceptability and feasibility. This 12-item Likert-type scale was adapted from the Digital Equipment Corporation

“System Usability Scale” (1986) and it will be administered to the Kiosk Group upon completion of the study.

6.6 Statistical Methods Planned in the Protocol and Determination of Sample Size

6.6.1 Statistical and Analytical Plans

The original analysis plan will be carried out using all available subject data points. No interim analysis will be performed. Exploratory data analyses will be conducted on the serum vitamin D levels of participants assigned to either the oral vitamin D supplementation or kiosk group. The analysis will be restricted to participants with valid baseline serum vitamin D data and at least one follow-up blood draw. The Shapiro-Wilk test will be used to assess the normality of the data distribution. Measures of central tendency and dispersion are provided for continuous data as medians (mdn) with associated interquartile ranges (IQR). Summary statistics will be provided for categorical variables and include the number of participants as well as the prevalence within each group.

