metabolism in 97.5% of the population.²⁰ While debate surrounds a sufficient range for 25(OH)D, there does seem to be a general acceptance that the optimum range is between 30 – 60 ng/mL.⁵⁻⁷ The human body uses sunlight as the primary source of vitamin D and produces large quantities efficiently with limited UVB exposure.¹²⁻¹⁵ Therefore, a rational way to determine the optimum vitamin D range is by studying natural cutaneous vitamin D synthesis. It has been demonstrated that a single session of full body exposure to solar radiation can produce a time-released equivalent of approximately 10,000 IU of oral vitamin D.¹⁶ A safe upper limit for vitamin D is related to oral intake only. Cutaneous vitamin D production is automatically regulated by a photochemical reaction and pigmentation, preventing toxicity.¹⁷⁻¹⁹ Consequently, hypervitaminosis D is not possible when the only vitamin D source is skin production following exposure to UVB light. For all these reasons, an innovative alternative to address low vitamin D status in adults, Warfighters included, is needed.

5 Study Objectives

The specific aims for this project were:

1. Determine acceptability and feasibility of a standing phototherapy kiosk designed as a self-care intervention for AD and retired service members, beneficiaries, and DA civilians;
2. Demonstrate that narrow spectrum UVB delivered by the SPK is at least equivalent to D3 oral intake to raise or maintain serum 25(OH)D levels over a 10-week intervention period;
3. Examine the relationship of demographic variables, including gender, age, body mass index, body fat, ethnicity, and sun exposure to serum 25(OH)D levels in both groups.

6 Investigational Plan

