All eligible adult volunteers will be enrolled regardless of their baseline 25(OH)D level as it is important in this non-inferiority study to show there is no potential for harm from phototherapy, even if the baseline 25(OH)D level is above 30 ng/mL. If the goal is to develop a self-care kiosk, individuals will not have the ability to check their serum vitamin D status prior to use. We also want to learn the trajectory of vitamin D absorption and availability over a 3-4-month period in order to make evidence-based therapeutic recommendations. It is not possible to blind the subjects or research team to the group assignment given the two comparators.

Serum levels of 25(OH)D, calcium, and parathyroid hormone are drawn at baseline (T0), immediately following the intervention at 10 weeks (T6); at 14 weeks (T8), 25(OH)D is drawn to document sustainment of treatment effect. Remuneration in the form of \$20 Amazon gift cards is provided to all volunteers after the baseline and final scheduled blood draw (as allowed by DoD Instruction 3216.02 Dated November 8, 2011).

A survey shall be completed at T1 and reviewed with participants again at the 10-week visit to capture relevant demographic, medical history, sun exposure, travel, daily activities, and dietary data. Active duty SMs shall report the number of days on profile (activity restriction) for the previous three months, at T1 and T6. A Device Usability Scale will be administered to the kiosk group participants upon protocol completion to address acceptability and feasibility of the treatment. With the assistance of a biostatistician, we will analyze data using repeated measures analysis of variance adjusting for significant covariates such as 25(OH)D level at baseline. Logistic regression analyses are used to predict outcomes and explain the interrelationships among variables, i.e. age, gender, BMI, body fat, ethnicity, and sun exposure relationship to 25(OH)D serum levels.

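### The plan names repeated measures ANOVA without saying which draws enter it or how a missing draw is handled; in its classical complete-case form it cannot deliver the analysis set that section 6.6.1 promises

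*Combined protocol and SAP*

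**What the plan says.** Section 6.6.1 makes two commitments. The first is "The original analysis plan will be carried out using all available subject data points". The second defines the analysis set: "The analysis will be restricted to participants with valid baseline serum vitamin D data and at least one follow-up blood draw". Section 6.5.1 sets out "two follow-up measurements, one at 10 weeks and a final level 4 weeks after completing the protocol", so the rule knowingly admits people who have only one of the two.

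Section 6.1 names the model: "we will analyze data using repeated measures analysis of variance adjusting for significant covariates such as 25(OH)D level at baseline". It is the only model named for comparing the arms; the logistic regressions in 6.1 and 6.4.7 concern relationships among covariates and 25(OH)D.

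On timing, section 6.5.3 says "Serum 25(OH)D level is the primary endpoint used to establish whether the treatment in the phototherapy kiosk group is equivalent" and gives no time point. Aim 2 in section 5 asks whether the kiosk can "raise or maintain serum 25(OH)D levels over a 10-week intervention period". Section 6.1 gives the later draw a supporting role: "at 14 weeks (T8), 25(OH)D is drawn to document sustainment of treatment effect".

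No section states the time points in the model, its covariance structure, its estimation method or a missing-data rule. Missing completely at random appears in the abbreviation list, and a test for it in the reference list, but the text invokes neither.

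**The concern.** A classical repeated measures ANOVA needs every repeated measure on every participant. With weeks 10 and 14 as the repeated outcomes, someone with a baseline and a week-10 value but no week-14 value belongs to the 6.6.1 analysis set, yet cannot contribute to the 6.1 model. The same holds for someone who missed week 10 but attended week 14.

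The first case matters more. Aim 2 is a 10-week question, and the week-14 draw comes four weeks after treatment ends. The number and mix of people who answer the 10-week question would depend on who returns for a later, off-treatment visit. The certain cost is precision; under specific conditions there is also bias.

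**Working it through.** **Inputs from the documents.** Section 6.6.2 gives a required sample of 60, a minimum enrollment of 78, a request for 120, and 30% attrition not split by visit. The 78 is reproduced as 60 × 1.30 = 78. That figure only sets the scale here; how attrition was applied to it is a separate matter.

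**Assumed.** The share *m* of participants with a week-10 value who miss week 14 is not in the documents. I take 5% to 30%.

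**Precision.** Week-10 values lost = N × m, where N is the number with a week-10 value. The standard error of the week-10 arm difference grows by 1/√(1 − m).

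| m | Lost of 60 | Lost of 78 | Lost of 120 | SE factor |
|---|---|---|---|---|
| 5% | 3 | 3.9 | 6 | 1/√0.95 = 1.03 |
| 10% | 6 | 7.8 | 12 | 1/√0.90 = 1.05 |
| 15% | 9 | 11.7 | 18 | 1/√0.85 = 1.08 |
| 20% | 12 | 15.6 | 24 | 1/√0.80 = 1.12 |
| 30% | 18 | 23.4 | 36 | 1/√0.70 = 1.20 |

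The columns for 78 and 120 assume nobody is lost before week 10. The SE factor does not depend on N.

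**Behaviour of the two methods.** In one simulated set of 60 participants, 19 of them without week 14, a standard repeated measures ANOVA routine rejected the data as unbalanced. The complete cases were 41 people (82 values), so 19 valid week-10 values were discarded. A mixed model on the same data kept all 60 people (60 + 41 = 101 values). The standard error of the week-10 difference was 1.39 for complete cases and 1.12 for the mixed model. The inputs are invented; this shows the mechanism, not an expected size.

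**Bias.** Assumed set-up: 40 per arm with a week-10 value, baseline to week-10 correlation 0.7, SD 6 or 8 ng/mL, 15% missing week 14, 4,000 simulated trials, baseline-adjusted week-10 difference in complete cases.

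| Who misses week 14 | SD 6 | SD 8 |
|---|---|---|
| Kiosk arm: from the lower half of its week-10 levels; supplement arm: not so related | about +0.4 | +0.5 to +0.6 |
| Lower half of week-10 levels, in both arms | 0.00 | +0.02 |
| Kiosk arm: related to baseline only | −0.02 | −0.06 |

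Using all week-10 values, the first scenario gives 0.00 (SD 6) and −0.03 (SD 8), and the third gives −0.02 and −0.05.

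A hand check on the first row: 15% of 40 is 6 people, taken from the lower 20. The mean of the lower half of a normal distribution is −0.798 SD and of the upper half +0.798 SD. The 34 who remain therefore have a mean shifted by (20 × 0.798 − 14 × 0.798)/34 = 0.141 SD. Adjusting for baseline removes the fraction 0.7² = 0.49, leaving 0.141 × 0.51 = 0.072 SD, which is 0.43 ng/mL at SD 6 and 0.57 at SD 8. This agrees with the simulation.

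Against the simulated standard errors, the shift is 0.40/1.07 = 0.37 of a standard error at SD 6 and 0.59/1.37 = 0.43 at SD 8.

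**The case against.** The strongest reply is that the plan never says incomplete participants are deleted. A reader might infer such a rule from the name of the model, but deletion is a property of the classical method. Section 6.6.1 could be read as the instruction for fitting the 6.1 model, and a mixed-model fit would keep everyone it admits. This stands, and it makes the point conditional. It does not remove the point, because nothing in the text selects that fit over the classical one.

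Second, section 6.1 does not say that both follow-up draws enter one model. An analysis of baseline and week 10 alone would lose nothing when week 14 is missed. That is also true. But with baseline as a covariate, as 6.1 proposes, two follow-up draws are needed for the outcome to be repeated at all, and 6.1 also states an interest in the trajectory over three to four months. If week 10 alone were used, a participant with only week 14 would be in the analysis set and contribute nothing, so a mismatch would remain.

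Third, week 10 is never declared the primary time point. It is a fair inference from Aim 2, and the gap is itself part of what needs repair.

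Two stronger readings are tempting. One is that any link between week-14 attendance and the week-10 level biases the comparison. The second and third scenarios above show that it need not, and nothing in the documents points to missingness that differs by arm in the required way. The other is that uneven spacing of the draws breaks sphericity. With baseline as a covariate only two repeated levels remain, so sphericity holds automatically, and uneven spacing does not by itself violate it.

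**Conclusion.** The plan is under-specified, and the plain classical reading of its named model conflicts with its own analysis set. The conflict requires two things that the documents leave open: a complete-case fit, and weeks 10 and 14 together as outcomes.

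Under those conditions the loss is 3 to 18 of 60 week-10 values, with a standard error about 3% to 20% larger, for an assumed 5% to 30% missing week 14. Bias is possible but not established: about +0.4 to +0.6 ng/mL toward the kiosk in one assumed scenario, and about zero if the mechanism is the same in both arms or depends on baseline only. The documents do not support a statement that the planned comparison is biased. For a pilot this is a defect worth correcting, not one that invalidates the design.

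**What to change.** In sections 6.1 and 6.6.1, replace the repeated measures ANOVA with a likelihood-based mixed model for repeated measures:

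- outcomes: 25(OH)D at week 10 and week 14;
- terms: baseline 25(OH)D, arm, visit, arm-by-visit and baseline-by-visit;
- unstructured covariance and Kenward-Roger degrees of freedom;
- the week-10 arm contrast declared primary, in line with Aim 2, and stated in section 6.5.3 as well.

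State that the model assumes data missing at random. Add one sensitivity analysis, for example a week-10 ANCOVA on all available week-10 values, log-transformed if residuals are skewed.

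The cost is some wording and a different procedure call, with no added visits or data. The downside is small: the model assumes missing at random and approximately normal residuals. Its missing-data assumption is weaker than the one a complete-case analysis needs. In particular, it allows week-14 attendance to depend on the observed week-10 value. The normality question is already raised by the Shapiro-Wilk test planned in 6.6.1, and the sensitivity analysis covers it.
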